7.2.2 SAE reporting

To ensure subject safety, every SAE, regardless of causality, occurring after the subject has provided informed consent and until 30 days after the last study visit must be reported to Novartis within 24 hours of learning of its occurrence. Any SAEs experienced after the 30 days period should only be reported to Novartis if the Investigator suspects a causal relationship to study treatment.

Recurrent episodes, complications, or progression of the initial SAE must be reported as follow-up to the original episode, regardless of when the event occurs. This report must be submitted

within 24 hours of the Investigator receiving the follow-up information. An SAE that is considered completely unrelated to a previously reported one should be reported separately as a new event.

Information about all SAEs (*either initial or follow up information*) is collected and recorded on the paper Serious Adverse Event Report Form. The Investigator must assess the relationship to *each specific component of study treatment (if study treatment consists of several drugs)* complete the SAE Report Form in English, and send the completed, signed form by fax within 24 hours after awareness of the SAE to the local Novartis Drug Safety and Epidemiology Department. The telephone and fax number of the contact persons in the local department of Drug Safety and Epidemiology, specific to the site, are listed in the investigator folder provided to each site. The original copy of the SAE Report Form and the fax confirmation sheet must be kept with the case report form documentation at the study site. Follow-up information should be provided using a new paper SAE Report Form stating that this is a follow-up to a previously reported SAE

Follow-up information provided should describe whether the event has resolved or continues, if and how it was treated, whether the treatment code was broken or not and whether the subject continued or withdrew from study participation. Each re-occurrence, complication, or progression of the original event should be reported as a follow-up to that event regardless of when it occurs.

If the SAE is not previously documented in the Investigator's Brochure or Package Insert (new occurrence) and is thought to be related to the investigational treatment a Drug Safety and Epidemiology Department associate may urgently require further information from the Investigator for Health Authority reporting. Novartis may need to issue an Investigator Notification (IN) to inform all Investigators involved in any study with the same investigational treatment that this SAE has been reported. Suspected Unexpected Serious Adverse Reactions (SUSARs) will be collected and reported to the competent authorities and relevant ethics committees in accordance with EU Guidance 2011/C 172/01 or as per national regulatory requirements in participating countries.

7.3 Pregnancy reporting

To ensure subject safety, each pregnancy occurring while the subject is on study treatment must be reported to Novartis within 24 hours of learning of its occurrence. The pregnancy should be followed up to determine outcome, including spontaneous or voluntary termination, details of the birth, and the presence or absence of any birth defects, congenital abnormalities, or maternal and/or newborn complications.

Pregnancy should be recorded on the Clinical Trial Pregnancy Form and be reported by the Investigator/qualified site staff to the local Novartis Drug Safety and Epidemiology Department. Pregnancy follow-up should be recorded on the same form and should include an assessment of the possible relationship to the study treatment.

Any SAE experienced during the pregnancy must be reported on the SAE Report Form.

8 Data review and database management

8.1 Site monitoring

At a site initiation visit or at an investigator's meeting, a Novartis representative will review the protocol and eCRFs with the Investigators and their staff. During the study, Novartis employs several methods of ensuring protocol and GCP compliance and the quality/integrity of the sites' data. The field monitor will visit the site to check the completeness of subject records, the accuracy of entries on the eCRFs, the adherence to the protocol and to Good Clinical Practice, the progress of enrollment, and to ensure that study treatment is being stored, dispensed, and accounted for according to specifications. Key investigator staff must be available to assist the field monitor during these visits. Continuous remote monitoring of each site's data may be performed by a CRO. Additionally, a CRO may analyze data and identify risks and trends for site operational parameters, and provide reports to the Novartis Clinical Team to assist with trial oversight.

The Investigator must maintain source documents for each subject in the study, consisting of case and visit notes (hospital or clinic medical records) containing demographic and medical information, laboratory data, electrocardiograms, and the results of any other tests or assessments. All information on eCRFs must be traceable to these source documents in the subject's file. The Investigator must also keep the original informed consent form signed by the subject (a signed copy is given to the subject).

The Investigator must give the monitor access to all relevant source documents to confirm their consistency with the eCRF entries. Novartis monitoring standards require full verification for the presence of informed consent, adherence to the inclusion/exclusion criteria, documentation of SAEs, and of data that will be used for all primary variables. Additional checks of the consistency of the source data with the CRFs are performed according to the study-specific monitoring plan. No information in source documents about the identity of the subjects will be disclosed.

8.2 Data collection

Designated investigator staff will enter the data required by the protocol into the Electronic Case Report Forms (eCRFs) using fully validated software that conforms to US 21 CFR Part 11 requirements. Designated investigator site staff will not be given access to the EDC system until they have been trained.

Automatic validation programs check for data discrepancies and, by generating appropriate error messages, allow the data to be confirmed or corrected online by the designated investigator site staff. The Investigator must certify via electronic approval that the data entered into the eCRFs are complete and accurate. After database lock, the Investigator will receive copies of the subject data for archiving at the investigational site.

8.3 Database management and quality control

A CRO working on behalf of Novartis will review the data entered into the eCRFs by investigational staff for completeness and accuracy and instruct the site personnel to make any required corrections or additions. Queries are sent to the investigational site using an electronic data query. Designated investigator site staff is required to respond to the query and confirm or correct the data.

Concomitant medications entered into the database will be coded using the WHO Drug Reference List, which employs the Anatomical Therapeutic Chemical classification system. Concomitant procedures, non-drug therapies and adverse events will be coded using the Medical dictionary for regulatory activities (MedDRA) terminology.

Laboratory samples (including cardiometabolic biomarkers) will be processed centrally and the results will be sent electronically to a designated CRO.

FDG-PET/CT scans will be read and analyzed centrally and the results will be sent electronically to a designated CRO.

A PRO questionnaire will be completed by the subject on paper, and the data transcribed into the eCRF by investigator site staff.

Randomization codes and data about all study drug(s) dispensed to the subject will be tracked using an Interactive Response Technology (IRT). The system will be supplied by a vendor, who will also manage the database. The database will be sent electronically to a designated CRO.

Each occurrence of a code break via IRT will be reported to the clinical team and monitor. The code break functionality will remain available until study shut down or upon request of Novartis.

The occurrence of relevant protocol deviations will be determined. After these actions have been completed and the database has been declared to be complete and accurate, it will be locked and the treatment codes will be unblinded and made available for data analysis. Any changes to the database after that time can only be made after written agreement by Novartis management.

8.4 Data Monitoring Committee

[figure not shown]
Not required.

8.5 Adjudication Committee

Not required.

9 Data analysis

A designated Contract Research Organization will perform the statistical analysis.

It is planned that the data from all centers that participate in this protocol will be combined, so that an adequate number of subjects will be available for analysis.

Unless otherwise specified, all statistical tests will be conducted against a two-sided alternative hypothesis, employing a significance level of 0.05.

Efficacy, safety, and other data will be summarized. For continuous variables, summary statistics (mean, standard deviation, median, 25th and 75th percentiles, interquartile range, minimum, and maximum) at each time point and for change from baseline to each time point will be reported by treatment group.

9.1 Analysis sets

The following analysis sets will be used for the statistical reporting and analyses:

Randomized Set: The randomized set includes all subjects who were randomized.

Safety Set: The Safety Set includes all subjects who received at least one dose of study medication. Subjects will be analyzed according to treatment received.

Full Analysis Set: The Full Analysis Set includes all subjects to whom study medication has been assigned. Subjects inappropriately randomized (e.g., IRT was called in error for randomization of a screen failed subject) will be excluded from this analysis set. Following the intent-to-treat principle, subjects will be analyzed according to the treatment they were assigned to at randomization.

9.2 Subject demographics and other baseline characteristics

Data will be summarized with respect to demographic and baseline characteristics for the Randomized Set and the Full Analysis Set.

9.3 Treatments

The number of subjects and the length of time (in days) exposed to each treatment will be summarized for the Safety Set. Note that during the Double-blind Treatment Period, all subjects will receive their last dose of study treatment at Visit 7/Week 8.

Concomitant medications will be summarized by treatment using frequency counts and percentages for the Safety Set.

Any condition entered as medical history or current medical condition at baseline will be coded using the MedDRA dictionary for the Safety Set. They will be summarized by system organ class and preferred term of the MedDRA dictionary. Summaries for cardiovascular and psoriasis-specific medical history will be provided as well.

9.4 Analysis of the primary variable

9.4.1 Variable

The primary efficacy variable is the change from baseline in the target (arterial vascular uptake) to background (venous blood pool) ratio from the aorta. Target to background ratio is considered the standard reporting variable based on FDG-PET/CT scans in vascular studies (see [Section 6.4.1](#)). The primary analysis time point will be at Week 12.

9.4.2 Statistical model, hypothesis, and method of analysis

Let μ_j denote the population mean of change from baseline in the target to background ratio from the aorta at Week 12 for treatment group j , $j = 0, 1$, where 0 corresponds to placebo and 1 corresponds to secukinumab.

The following null hypothesis (H_0) will be tested against the alternative hypothesis (H_A):

$$H_0: \mu_1 - \mu_0 = 0$$

$$H_A: \mu_1 - \mu_0 \neq 0$$

The primary efficacy variable will be analyzed by an analysis of covariance (ANCOVA) model with treatment, baseline, and body weight (<90 kg, \geq 90 kg) as explanatory variables. The least squares means of the two treatment groups, least squares mean difference of the treatment groups, 95% confidence interval for the difference in the two treatment groups, and p-value based on the fitted linear model will be reported.

The primary analysis of the primary efficacy variable will be based on the Full Analysis Set.

9.4.3 Handling of missing values/censoring/discontinuations

Missing data will be imputed using the last-observation-carried-forward (LOCF) method. If a subject has no post-baseline value, the missing value will not be imputed and the subject will be removed from the analysis.

9.4.4 Supportive analyses

A supportive nonparametric analysis will be performed to examine the consistency of results if the assumption of normality for the distribution of the primary efficacy variable is not tenable. For this supportive analysis, the primary efficacy variable will be analyzed using the stratified Wilcoxon rank-sum test with modified ridit scores (van Elteren's test), adjusting for body weight (<90 kg, \geq 90 kg) ([Stokes, Davis, and Koch, 2012](#)).

9.5 Analysis of secondary variables

9.5.1 Efficacy variables

The secondary efficacy variables are the following:

- Change from baseline in each biomarker (see [Section 6.4](#))
- PASI 75 response (yes, no)
- PASI 90 response (yes, no)
- PASI 100 response (yes, no)
- IGA mod 2011 score of 0 or 1 (yes, no)
- Change from baseline in DLQI total score

Change from baseline in each biomarker and change from baseline in DLQI total score will be analyzed at each time point using the same ANCOVA model as for the primary efficacy variable, and missing data will be imputed using the LOCF method.

IGA mod 2011 score of 0 or 1 and PASI 75 / 90 / 100 responses will be analyzed at each time point using the Cochran-Mantel-Haenszel test to compare secukinumab and placebo, adjusting for body weight (<90 kg, ≥90 kg) ([Stokes, Davis, and Koch, 2012](#)). A 95% confidence interval for the difference between the two treatment groups in the proportion of subjects who are responders will be calculated using the normal approximation to the binomial distribution. For response (yes, no) at Week 12 (and other time points), a subject with a missing assessment will be considered as a responder (yes) if the subject meets the response criterion at the time of premature discontinuation from the study. Otherwise, the subject will be considered as a non-responder (no).

Analyses of the secondary efficacy variables will be based on the Full Analysis Set.

9.5.2 Safety variables

The assessment of safety will be based mainly on the frequency of adverse events and laboratory data. Other safety data (e.g., vital signs and special tests) will be considered, as appropriate.

Adverse events will be summarized by presenting, for each treatment group, the number and percentage of subjects having any adverse event, having an adverse event in each body system and having each individual adverse event. Any other information collected (e.g., severity or relatedness to study medication) will be listed, as appropriate.

Adverse events and serious adverse events up to and including the Week 12 visit will be included in the database for the analysis at the primary analysis time point (Week 12).

Laboratory variables will be summarized.

Analysis of safety data will be based on the Safety Set.

9.5.3 Resource utilization

Not applicable

9.5.4 Pharmacokinetics

Not applicable.

9.5.5 Pharmacogenetics/pharmacogenomics

Not applicable.

9.5.6 Other biomarkers

Not applicable.

9.5.7 PK/PD

Not applicable.

9.6 Interim analyses

The primary analysis at Week 12 is considered an interim analysis. As Week 12 is the primary analysis time point, no adjustment to the significance level of 0.05 will be made.

9.7 Sample size calculation

The sample size was based on change from baseline in the target (arterial vascular uptake) to background (venous blood pool) ratio (TBR) from the aorta. Using a t-test, a clinically important mean treatment difference of 0.15, a (common) standard deviation (SD) of 0.196, an allocation ratio of 1:1, a two-sided significance level of 0.05, and a power of 0.90, it was determined that approximately 74 subjects (37 in each treatment group) are necessary (nQuery Advisor 7.0) (Bissonnette et al 2013; Tawakol et al 2013). Without adjusting for multiplicity, the sample size of 74 subjects will also provide at least 0.90 power for other biomarkers (see Section 6.4.2) if the treatment difference is 0.76 SD or smaller. The general threshold for clinical importance is 1 SD. Allowing for a loss to follow-up rate of 0.10, approximately 84 subjects (42 in each treatment group) will be randomized.

10 Ethical considerations

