### **2.5.2 Statistical hypothesis, model, and method of analysis**

The primary efficacy variable will be analyzed by an analysis of covariance (ANCOVA) model with treatment, baseline, and body weight (<90 kg, ≥90 kg) as explanatory variables.

Following null hypothesis ( $H_0$ ) will be tested against the alternative hypothesis ( $H_A$ ):

$$H_0: \mu_1 - \mu_0 = 0$$

$$H_A: \mu_1 - \mu_0 \neq 0$$

where  $\mu_1$  and  $\mu_0$  denote the population mean of change from baseline in the target to background ratio from the aorta at Week 12 for secukinumab group and placebo group, respectively.

The least squares means of the two treatment groups, least squares mean difference, and 95% confidence interval for the difference in the two treatment groups will be presented along with the p-value based on the fitted linear model.

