## **2.7.2 Statistical hypothesis, model, and method of analysis**

### **2.7.2.1 Cardiometabolic Biomarkers**

Change from baseline in each cardometabolic biomarker, described in Section 2.12, will be analyzed at each time point using the same ANCOVA model as for the primary efficacy variable.

In addition, change from the baseline in each biomarker will be analyzed using the stratified Wilcoxon rank-sum test with modified ridit scores (van Elteren's test), adjusting for body weight (<90 kg, ≥90 kg) (Stokes, Davis, and Koch, 2012) if the normality assumption for the variable is not tenable. The analysis will be based on Full Analysis Set.

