## 3 Sample size calculation

The sample size was based on change from baseline in the target (arterial vascular uptake) to background (venous blood pool) ratio (TBR) from the aorta. Using a t-test, a clinically important mean treatment difference of 0.15, a (common) standard deviation (SD) of 0.196, an allocation ratio of 1:1, a two-sided significance level of 0.05, and a power of 0.90, it was determined that approximately 74 subjects (37 in each treatment group) are necessary (nQuery Advisor 7.0) (Bissonnette et al, 2013; Tawakol et al, 2013). Without adjusting for multiplicity, the sample size of 74 subjects will also provide at least 0.90 power for other biomarkers if the treatment difference is 0.76 SD or smaller. The general threshold for clinical importance is 1 SD. Allowing for a loss to follow-up rate of 0.10, approximately 84 subjects (42 in each treatment group) will be randomized.

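### The biomarker power statement runs the wrong way: with 37 per arm, power reaches 0.90 at about 0.764 SD and above, not at 0.76 SD and below

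*Protocol*

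**What the plan says.** Protocol 9.7 sizes the trial on the change in aortic TBR: "Using a t-test, a clinically important mean treatment difference of 0.15, a (common) standard deviation (SD) of 0.196, an allocation ratio of 1:1", two-sided 0.05 and power 0.90. This gives 37 evaluable subjects per arm, or 74 in all, raised to 84 randomised for 10% loss to follow-up.

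The same paragraph then extends the result to the biomarkers, without multiplicity adjustment. It says the 74 subjects "will also provide at least 0.90 power for other biomarkers (see Section 6.4.2) if the treatment difference is 0.76 SD or smaller", and adds: "The general threshold for clinical importance is 1 SD".

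The data analysis part of the Protocol summary repeats the claim, and SAP Section 3 carries the same condition, "if the treatment difference is 0.76 SD or smaller". Neither document corrects it or states the opposite direction.

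For the analysis itself, SAP 2.7.2.1 has each biomarker analysed "using the same ANCOVA model as for the primary efficacy variable". For that model, SAP 2.5.2 says a "95% confidence interval for the difference in the two treatment groups will be presented".

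**The concern.** For a fixed sample size and significance level, the power of a two-sided t-test increases with the size of the true difference. As the difference shrinks to zero, power falls to the significance level, 0.05. A statement that power is at least 0.90 for every difference up to a limit therefore cannot be true, whatever the limit.

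This is the only statement of power for the cardiometabolic biomarkers, which are a stated secondary objective and are to be analysed one by one (SAP 2.12). A reader who took it at face value could treat a non-significant biomarker result as good evidence against a moderate effect. At a true difference of 0.5 SD the test would miss the effect about 44% of the time (1 − 0.564).

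**Working it through.** **Inputs** (all from Protocol 9.7): difference 0.15, SD 0.196, 1:1 allocation, two-sided 0.05, power 0.90, 37 evaluable per arm, no multiplicity adjustment for the biomarkers.

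**Formula.** For n per arm and standardised difference d, the test statistic has a noncentral t distribution with df = 2n − 2 and noncentrality λ = d·√(n/2). Power = P(T > c) + P(T < −c), where c = t(0.975, df).

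**Step 1: reproduce the plan's sample size.** d = 0.15/0.196 = 0.7653. At 37 per arm power is 0.9010; at 36 per arm it is 0.8929. So 37 per arm is confirmed. Allowing for dropout, 37/0.90 = 41.1, rounded up to 42 per arm, or 84 in all, as stated.

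**Step 2: find the difference at which power is 0.90 with 37 per arm.** Solving the formula gives d = 0.7639. The normal approximation, (1.960 + 1.282)·√(2/37), gives 0.754. The figure of 0.76 is therefore recovered, but as the smallest difference with 0.90 power.

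**Step 3: power on either side of it (37 per arm).**

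| True difference (SD) | Power |
|---|---|
| 0.2 | 0.136 |
| 0.5 | 0.564 |
| 0.6 | 0.721 |
| 0.7 | 0.844 |
| 0.76 | 0.897 |
| 0.77 | 0.9045 |
| 1.0 | 0.989 |

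The 0.897 at exactly 0.76 SD is a rounding matter and not the complaint.

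**Step 4: try assumptions kinder to the statement.**

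- All 42 per arm contribute: 0.90 is reached at 0.716 SD, and power at 0.5 SD is 0.620.
- Gain from baseline adjustment: the documents give no correlation between baseline and change, so I assumed r from 0.3 to 0.5 and replaced d by d/√(1 − r²) at 37 per arm. The 0.90 point moves to 0.7639·√(1 − 0.09) = 0.729 SD (r = 0.3) or 0.7639·√(1 − 0.25) = 0.662 SD (r = 0.5). Power at 0.5 SD is 0.604 or 0.688.
- One-sided 0.05 test at 37 per arm: power at 0.5 SD is 0.686.

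The threshold moves, but power still falls below it in every case.

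**Step 5: precision.** The 95% confidence interval half-width at 37 per arm is t(0.975, 72)·√(2/37) = 1.993 × 0.2325 = 0.463 SD.

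**The case against.** The best defence is that this is one wrong word whose intent is plain. The number matches the primary effect size, and the next sentence puts clinical importance at 1 SD, where power is 0.989. The authors evidently meant that the trial can detect differences as small as about 0.76 SD, comfortably inside that threshold. No decision rule, alpha allocation or analysis depends on the sentence, SAP 2.6 says there is no key secondary objective, and a confidence interval is already planned for each biomarker. On this view the correction is editorial, the number should stay at 0.76, and power at 0.5 SD need not be reported because the plan never names that difference.

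Much of this stands. The slip is probably one of wording, the consequence is limited to interpretation, and the added figure at 0.5 SD is optional. What does not stand is leaving the sentence alone. It conditions on the treatment difference itself, not on the detectable difference, so it makes a false quantitative claim, and it does so in the sample size sections of both governing documents as well as in the summary. On the number, keeping 0.76 would be defensible as rounding, but 0.77 makes the words *at least* literally true for the t-test the protocol names.

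**Conclusion.** The statement is wrong as written and should be corrected. With 37 per arm and a two-sided 0.05 t-test, power is at least 0.90 for true differences of about 0.764 SD or more, and below 0.90 for anything smaller. The direction of the error depends on no assumption. The exact threshold does: it ranges from 0.66 to 0.76 SD across the cases examined, the lower end resting on an assumed baseline correlation of 0.5.

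The effect is confined to a misstated power for the biomarkers. The sample size rests on TBR alone and reproduces, and the validity of the trial is not in question. Non-significant biomarker results should be read from their confidence intervals, which at about ±0.46 SD would often leave a moderate effect open.

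**What to change.** In Protocol 9.7, the Protocol summary and SAP Section 3, change the condition from 0.76 SD or smaller to *0.77 SD or larger*. It would help to add: *power is about 0.56 at 0.5 SD*. The sentence on the 1 SD threshold can stay and then reads consistently with what precedes it.

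The cost is wording in three places. The number of subjects, the primary analysis, the biomarker model and the planned tests do not change. The sponsor gives up only the claim of high power for small differences, and keeps power of 0.99 at its own threshold for clinical importance.
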